The study includes enumeration of all households in probability selected geographical units (national census enumeration areas) in catchment villages of selected health facilities, about 12-16 per intervention group. All households with resident caregivers of children 0-24 months of age will be eligible for recruitment into the caregiver cohort. Data collection includes two stages of recruitment/participation at baseline, whereby an eligible caregiver will complete a radio listenership survey during the household enumeration exercise, and will then be recruited into the caregiver cohort at a separate visit. Those consenting to the caregiver cohort will complete a detailed home-based caregiver survey at baseline and the same people will complete the listenership and caregiver surveys at endline. Table 1 provides an overview summary of data gathering activities.

[figure not shown]

Figure 2b. Research design overview – community health worker component

Table 1. Data gathering activities

Abbreviated Objective	(1) Caregiver radio listenership patterns, exposures, and effect on caregiver ECD perceptions, knowledge and reported parenting practices nine months post-intervention	(2) Effect of Malezi II full intervention (MRV-CCD) on caregiver's knowledge and parenting behaviors/practices compared to MR intervention	(3) Effect of short video job aids on the quality of counseling provided by the CHW in the clinic and the home (4) CHW perspectives and experiences with use of the short videos as a job aid (5) Caregiver perspectives and experiences with CHWs, short videos, and ECD services in the health facility.
Design	Two-arm pre/post intervention cohort(s) design About 30 health facility catchment communities (1) 12-16 facilities – MR intervention (radio messaging only) (2) 12-16 facilities – MRV-CCD augmented intervention (radio, video job aids, CCD package)		Pre/post cohort, intervention MRV-CCD group only 12-16 health facility catchment communities selected for the Malezi II evaluation study in MRV-CCD group Qualitative component with CHW FGDs and caregiver IDIs

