The outcome parameters used for sample size calculations for objectives 1 and 2 are estimated from the Malezi I program evaluation baseline data (before introduction of CCD program), comparable to what we would expect in the MR intervention group, who have not been exposed to any CCD intervention. From 24-29% of caregivers reported having a local or shop toy in the home, 22% reported singing to the child in the past month, and 7-13% reported reading or writing with the child in the past week.

Objective 1: To determine caregiver radio listenership patterns at baseline, and exposures to the ECD radio messaging nine months' post-intervention, and effect of radio exposure on caregiver ECD perceptions, knowledge and reported parenting practices, using pre-post surveys in a cohort of caregivers of children 0-24 months of age at baseline, in study communities from each intervention arm.

A sample size of 593 enrolled in the MR intervention group will provide 80% to detect a 5% or greater change from baseline (10%) to endline (15%) in the MR intervention group, taking into account 15% LTFU, design effect of 1.2, and estimated correlation of 0.4 between respondents at baseline and endline (Table 3). This sample size will provide even greater power to detect a 10% difference if baseline estimates are higher than 10%.

Table 3. Sample size estimation* parameters, MR group, caregiver cohort, pre-post

Arm	Prevalence of key outcome			Power	Sample size	Adjusted Sample size (15% LTFU, DE 1.2)
	Baseline	Endline	Expected Change			
MR (Malezi radio)	10%	15%	5%	80%	420	593
	20%	30%	10%	99%	419	592
	25%	35%	10%	98%	411	580

*STATA 14 paired proportions large-sample McNemar's test at 5% level significance.

Objective 2: To determine whether the Malezi II full intervention (MRV-CCD) significantly increases caregiver's knowledge and parenting behaviors/practices when compared to radio messaging alone, using a pre-post quasi-experimental evaluation design in a cohort of caregivers of children 0-24 months of age at baseline, in MRV-CCD and MR communities.

The change between baseline and endline in the Malezi I evaluation for the above-mentioned indicators ranged from 10-30% after introduction of the Malezi I CCD program. With the introduction of radio messaging only, we estimate a 5-10% effect size, and about a 20-30% effect size in the full intervention (MRV-CCD) group (Table 4).

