We estimate that a sample size of n=430 caregivers per intervention group will provide 90% power to detect a 15% "difference-in-differences" between the MR and MRV-CCD intervention groups at endline, and >80% power to detect a 5% change in the MR intervention group, and a 20% change in the MRV-CCD intervention group between baseline and endline, at a level of 5% significance. Taking into account a 15% non-retention rate and a design effect of 1.2, we will aim to enroll 1214 into the caregiver cohort or n=607 in each intervention group.

Table 4. Sample size estimation* parameters, MR compared to MRV-CCD groups, caregiver cohort, pre-post and differences-in-differences

Arm	Prevalence of key outcome			Power	Sample size	Adjusted Sample size (15% LTFU, DE 1.2)
	Baseline	Endline	Expected Change			
MR (Malezi radio)	10%	15%	5%	81%	430	607
MRV-CCCD (Malezi radio + radio + CCD program)	25%	45%	20%	>99%	430	607
Difference	15%	30%	15%	90%	860	1214

*Sample Size and Power estimated by a simulation of the DID Analysis using R Software Package.

Objective 3. To determine whether the introduction of short video job aids (training, provision, supportive supervision) to the Malezi II CCD program improves the quality of counseling provided by the CHW in the clinic and the home, using pre-post observation fidelity checklists for all CHWs working in the MRV-CCD communities.

The Malezi I evaluation assessed CHW-reported time spent in the home providing ECD messages to pregnant women or caregivers of children under 5 at baseline (14-17%) and endline (64-74%). While the change was substantial, we estimate that the actual CHW counseling skills would be lower using an observation checklist compared to CHW self-reported behaviors. We conservatively estimate that CHWs in the MRV-CCD intervention group, already trained in the Malezi I CCD program, will score at 50% on the baseline observation checklists in this evaluation, increasing 15-20% after introduction and capacity building in using the short videos.

Table 5 shows that a sample size of 123 CHWs will achieve 80% power to detect a 15% change between baseline and endline in CHW quality of counseling checklist score, taking into account a correlation of 0.4 between measures, a 5% non-retention rate and a design effect of 1.1.

Table 5. Sample size estimation* parameters, MRV-CCD CHW cohort, pre-post

Arm	Prevalence of key outcome			Power	Sample size	Adjusted Sample size (5% LTFU, DE 1.1)
	Baseline	Endline	Expected Change			

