Descriptive statistics (range, median, mean, percent) will be used to review the data overall and describe participant background characteristics, radio listenership patterns and parenting perceptions, knowledge and practices, identifying any baseline differences in population by study group. Confidence intervals (CI) will be calculated around summary measures and statistical tests of significance (non-parametric) will be applied where appropriate to compare the distribution of characteristics or outcomes across study groups. The effects of radio exposure only (objective 1) will be described by comparing study outcomes at baseline and endline within the MR study group only. Within study group differences in study outcomes will be described comparing distributions of responses to key outcome variables at baseline and endline using statistical testing appropriate for paired groups such as the paired t-test, Wilcoxon or McNemar's tests. Regression modelling may be used to estimate the intervention effect while controlling for covariates.

The additional effects of the combined exposure to radio, short videos and Malezi CCD (MRV-CCD; objective 2), as compared to the radio only effect, will be described using a differences in differences (DID) analysis. The treatment effect can be found by obtaining the proportion of caregivers with the outcome in the MRV-CCD and MR groups at both time periods. The difference in outcomes between study groups at both time periods may be charted to visualize the DID as shown in Figure 4, whereby the DID is what remains after subtracting the baseline differences between the two groups from the endline differences (30-5% = 25%). This will give an estimate of the extent of the improvement by the Malezi II full intervention. We will use regression modelling to estimate the intervention effect while controlling for covariates. We will use the following general form model:

$$Y = \beta_0 + \beta_1[\text{Intervention}] + \beta_2[\text{Time}] + \beta_3[\text{Intervention} \cdot \text{Time}] + \beta_4[\text{Covariates}] + \varepsilon$$

The interaction term coefficient β_3 will also estimate the extent of the DiD.

[figure not shown]

Figure 4. Differences in differences analysis graphic

Objective 3: Community Health Worker Cohort

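### The Objective 2 difference-in-differences model does not link a caregiver's two surveys or name who enters each proportion; fitted as printed at correlation 0.4, its standard error is about 23% too large, or about 13% after the design effect

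*Protocol*

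**What the plan says.** The Methodology section describes a caregiver cohort in which "the same people will complete the listenership and caregiver surveys at endline". In Data Analysis, Objectives 1 and 2: Caregiver Cohort, change within a study group is to be assessed "using statistical testing appropriate for paired groups such as the paired t-test, Wilcoxon or McNemar's tests".

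For Objective 2 the same section obtains the treatment effect by "obtaining the proportion of caregivers with the outcome in the MRV-CCD and MR groups at both time periods". It then says "We will use the following general form model" and prints Y as a function of intervention, time, intervention by time, and covariates, plus a single error term. The interaction coefficient is the difference-in-differences (DID). No caregiver or enumeration-area term is printed, and neither an analysis set nor a standard-error method is given for the DID.

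Sample Size Calculations, Objective 1, is based on "taking into account 15% LTFU, design effect of 1.2, and estimated correlation of 0.4 between respondents at baseline and endline". For Objective 2 it says: "Taking into account a 15% non-retention rate and a design effect of 1.2, we will aim to enroll 1214 into the caregiver cohort", that is, 607 per arm. Sampling within Study Communities makes the enumeration area the sampling unit.

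**The concern.** The same people answer twice, so a caregiver's two answers are correlated and part of the sampling error cancels in the change. A model with independent errors treats the two rounds as separate samples and reports too large a standard error. The between-arm estimate is then the one caregiver analysis that gives up the precision for which a cohort was recruited. The missing enumeration-area term works in the opposite direction, so the printed model leaves out two features that the sample size section counts.

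The second issue is who is analysed. With 15% non-retention planned, fitting the model to every collected survey and fitting it to completers only are different analyses. They can give different answers if the caregivers who leave differ from those who stay, and differ more in one arm than in the other. The arms are in different districts and are not randomised, so equal patterns of loss cannot be taken for granted.

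**Working it through.** **Inputs.** Table 4: MR 10% to 15%, MRV-CCD 25% to 45%, a DID of 20 − 5 = 15 points. Enrolled: 607 per arm. Retained: 607 × 0.85 = 516. Design effect: 1.2. Correlation ρ: 0.4 is stated for Objective 1 only, so for the DID it is an assumption and a range is shown. Loss is random in steps 1 to 3.

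**1. The plan's own figures.** 430 × 1.2 / 0.85 = 607.06, which reproduces 607. For the MR row at ρ = 0.4, P(yes, yes) = 0.10 × 0.15 + 0.4 × √(0.0900 × 0.1275) = 0.0578. The discordant proportions are therefore 0.0422 and 0.0922, with sum D = 0.1343 and difference d = 0.05. McNemar power at n = 430 is Φ[(d√n − 1.96√D) / √(D − d²)] = Φ(0.318/0.363) = 81%, as printed. At ρ = 0 it would be 60%, so this row evidently uses the pairing. The 90% DID power does not reproduce: a normal approximation on the proportion scale gives 97.1% at ρ = 0 and 99.9% at ρ = 0.4. It came from a simulation whose settings are not given, so this is not counted as an error.

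**2. Standard error reported by the printed model.** With p(1−p) of 0.0900, 0.1275, 0.1875 and 0.2475, the pooled residual variance is [607 × (0.0900 + 0.1875) + 516 × (0.1275 + 0.2475)] / (2 × 1123) = 0.1611. SE = √[0.1611 × (2/607 + 2/516)] = 0.0340.

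**3. True standard deviation of the same estimate.** Summed over arms, the variance is p0(1−p0)/607 + p1(1−p1)/516 − 2ρ√[p0(1−p0)p1(1−p1)]/607. The first two terms total 0.001184. The square roots are 0.1071 and 0.2154, so the last term totals 2ρ × 0.3225/607. At ρ = 0.4 the variance is 0.001184 − 0.000425 = 0.000759 and the SD is 0.0275.

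| ρ | True SD | 0.0340 / SD | SD × √1.2 | 0.0340 / (SD × √1.2) |
|---|---|---|---|---|
| 0.4 | 0.0275 | 1.23 | 0.0302 | 1.13 |
| 0.3 | 0.0294 | 1.16 | 0.0322 | 1.06 |
| 0.2 | 0.0312 | 1.09 | 0.0341 | 1.00 |
| 0 | 0.0344 | 0.99 | 0.0377 | 0.90 |

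At ρ = 0.4 the 95% half-width is 1.96 × 0.0340 = 6.7 points. It should be 5.4 without, or 5.9 with, the design effect. Ignoring clustering, a nominal 95% interval then covers 98.4% of the time.

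**4. Who enters each proportion.** Let L be the loss in an arm and g the baseline prevalence in leavers minus that in stayers. Using all baseline surveys instead of completers shifts the DID by L(MR) × g(MR) − L(MRV-CCD) × g(MRV-CCD). This is zero when L × g is equal in the two arms. With 15% loss in each arm and a 10-point difference in g between arms, the shift is 1.5 points. The documents give no g, so the patterns below are assumptions.

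- *Pattern A.* In MRV-CCD, 18% of those without the practice at baseline and 6% of those with it are lost: 0.75 × 0.18 + 0.25 × 0.06 = 15%. Loss in MR is random. Stayers' baseline is 0.25 × 0.94/0.85 = 27.6%. With P(yes, yes) = 0.25 × 0.45 + 0.4 × 0.2154 = 0.1987, their endline is (0.2513 × 0.82 + 0.1987 × 0.94)/0.85 = 46.2%. All available surveys give 46.2 − 25 − 5 = 16.2 points and complete pairs give 13.6, against a true 15. A random-intercept model on all surveys averages about 15 in simulation.
- *Pattern A in both arms.* The error with all surveys falls to 0.6 points.
- *Pattern B.* MRV-CCD leavers have 10% baseline prevalence and everyone changes equally. Stayers have (0.25 − 0.15 × 0.10)/0.85 = 27.6%. All surveys overstate the DID by 2.6 points and complete pairs are correct. A random-intercept model gave 16.7 in 60 simulated trials.

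**The case against.** The strongest reply is that the equation is offered only as a general form. It does not rule out a caregiver random effect or clustered standard errors, and the analysis set may be left to a statistical analysis plan that is not shown. The last part is fair: an unnamed analysis set would not be a finding by itself. But the protocol does commit to a model, and the model as written does not fit the cohort it describes or the paired methods a paragraph earlier.

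It is also true that the imprecision is conservative, that ρ = 0.4 is not stated for Objective 2, and that the missing enumeration-area term offsets part of the excess. At ρ = 0.2 with design effect 1.2 the two omissions cancel, and at lower ρ the interval is too narrow. That offset is accidental and does not make the model right.

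Three stronger readings are tempting and not supported:

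- A reader might infer that the plan sets all enrolled caregivers at baseline against only the retained ones at endline. No section says so. The quoted words fit a completer analysis equally well, and Table 4 uses one sample size for both rounds.
- A reader might infer that the 15% loss biases the DID. It does so only if loss is related to the outcome and differs by arm.
- A reader might argue that loss must differ because only MRV-CCD caregivers have home contact. The Intervention Description makes community health worker home visits part of the national standard in all study districts, and the cohort surveys are done at home in both arms. Only the research-observed counselling visits and the Malezi package are specific to MRV-CCD.

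**Conclusion.** The point holds as a mismatch between the printed Objective 2 model and the cohort design. Fitted as printed with independent errors, at the Table 4 rates and random 15% loss, the standard error is about 23% too large at ρ = 0.4, 16% at 0.3 and 9% at 0.2. With the design effect of 1.2 applied to the true variance, about 13% remains at ρ = 0.4.

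The effect of loss on the estimate cannot be fixed from the documents. Shifts of 1 to 3 points follow from assumed patterns that differ by arm, and similar loss in both arms largely cancels. This is a correction worth making before analysis. It does not show that the DID is biased.

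**What to change.** Replace the printed Objective 2 model with a repeated-measures form for the same difference in proportions. Use either a caregiver random intercept or GEE with an exchangeable working correlation, with standard errors that also account for the enumeration area. Caregivers sit within enumeration areas, and about 250-300 areas are planned, so standard errors clustered on the area can cover both levels.

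State that the model is fitted to all available surveys. Report the complete-pairs DID beside it as a sensitivity analysis, with loss and the leavers' baseline outcomes by arm.

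The caregiver term should not be presented as a cure for attrition. It corrects the precision and helps when loss depends on the observed baseline outcome (pattern A), but it leaves bias in pattern B, where complete pairs do better. That is why both estimates should be shown.

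The cost is a revised model statement, one sentence on the analysis set and one table. No new data are needed, because the participant identification number already links the surveys.
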